4.4. Efficacy Estimand Analysis

The efficacy endpoints assessment, guided by the "efficacy estimand," will be conducted using the EAS. For the "efficacy estimand," the hypothetical strategy is used to handle the ICEs, so only data collected before the occurrence of any such ICEs will be used in the estimation. Subjects who received only the first dose will be considered to be "on-treatment" during Day 1 to Day 180, whereas subjects who received both doses will be considered to be on-dose during the entire treatment and assessment period (Day 1 to Day 540).

The ICEs considered in the analysis, which are "permanent discontinuation of intervention" and "initiation of excluded medications taken during the study and new initiation of Lp(a) altering therapies per the protocol inclusion criteria", will be handled by the hypothetical strategy, and the potential outcome of interest is the response in the efficacy measurement if participants had adhered to the randomized treatment without using such medication (medication list in Table EZEB.4.4 based on known impact on Lp[a]). Analyses post–Day 180 will also consider the ICE of "treatment discontinuation." There are no other defined ICEs. Switching medications within a class (for example, from 1 statin to another) is not considered as an ICE for the definition of estimand in this study.

Category	Medication	
Lp(a)-Altering Therapies	 statins PCSK9 inhibitors prescription-dose niacin mipomersen testosterone, estrogens, antiestrogens, progestins, selective estrogen receptor modulators, or growth hormone 	
Excluded Treatment Medical Devices, and/or Procedures	 lipid apheresis any investigational drug, biological agent, or device other than study provided investigational product 	

Abbreviation: Lp(a) = lipoprotein(a).

4.4.1. **Definition of Endpoint(s)**

The following endpoints will be analyzed with the "efficacy estimand" using the data in the EAS:

- percent change from baseline in time-averaged Lp(a) over Days 60 to 180, Days 240 to 360, Days 30 to 180, and Days 30 to 360
- proportion of participants achieving Lp(a) <125 and <75 nmol/L at Days 60, 180, 240, 360, and 540
- proportion of participants achieving time-averaged Lp(a) <125 and <75 nmol/L over Days 30 to 180 and Days 30 to 360
- percent change from baseline and absolute change from baseline to Days 60, 180, 240, 360, and 540 for
 - o Lp(a)
 - apolipoprotein B (ApoB), and
 - high-sensitivity C-reactive protein (hsCRP)
- proportion of participants achieving Lp(a) lowering of at least 150 nmol/L at Days 60, 180, 240, 360, and 540
- proportion of participants achieving time-averaged Lp(a) lowering of at least 150 nmol/L over Days 30 to 180 and Days 30 to 360
- percent change from baseline and absolute change from baseline in low-density lipoprotein-cholesterol (LDL-C), total cholesterol, high-density lipoprotein-cholesterol (HDL-C), and triglyceride (TG)

The Day 60 and Day 180 analyses may also pool the 2 LY3819469 400-mg treatment groups, where appropriate.

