Endpoint: percent change from baseline in time-averaged Lp(a) over Days 60-180 which will be calculated by area under the curve (AUC) between Day 60 to Day 180 divided by 120.

Treatment condition: the randomized treatment with allowance for safety. Further details on study interventions, and concomitant interventions can be found in Section 6.

There are no intercurrent events. Since each patient can only take one dose for the first 6 months, there is no intercurrent events of treatment discontinuation. The concomitant medication use is not considered intercurrent events as it is considered as a part of patient management.

Population-level summary: mean percent changes in Lp(a).

Treatment contrast of interest: difference in mean percent changes in Lp(a) between LY3819469 and placebo.

Rationale for estimand: this estimand aims to study the efficacy of LY3819469 that reflects the real-life behavior of the target population.

Estimand(s) for secondary objective

A similar estimand for the primary objective will be used for the secondary clinical response before the second injection at Day 180. For the objectives after Day 180, the treatment discontinuation will be handled by treatment policy strategy.

Unless specified otherwise, safety assessments will be guided by an estimand comparing safety of LY3819469 doses with placebo irrespective of adherence to study intervention.

4. Study Design

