#### 9.3.3. Secondary Endpoint(s)/Estimand(s) Analysis

Secondary endpoints are listed in Section 3.

The efficacy analyses for the secondary endpoints will use the FAS described in Section 9.3.1. and may also pool the two LY3819469 400-mg treatment groups, where appropriate.

Analyses for percent change from baseline in time-averaged Lp(a) over Days 240-360 will be conducted in a manner similar to the primary efficacy analysis discussed in Section 9.3.2.

The continuous clinical measures, including Lp(a), ApoB, and hsCRP, may be log transformed before statistical analyses, if deemed necessary. Analyses for change from baseline in each log-transformed parameter at Days 60, 180, 240, 360, and 540 will be conducted using mixed model for repeated measures (MMRM). The percent change from baseline will be calculated and reported by exponentiating the estimates for the change from baseline in above model.

Analyses for percentages of participants reaching Lp(a) <125 nmol/L and <75 nmol/L at Day 60, 180, 240, 360, and 540 will be conducted using logistic regression modeling.

In these models, additional covariates may be added, if deemed necessary. The details will be provided in the SAP.

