4.2. Participant Dispositions

A listing and summary of study disposition for all randomized participants will be provided at the primary database lock and final database lock, respectively. Frequency counts and percentages of all participants screened, randomized, and receiving at least 1 dose of study drug will be presented by treatment groups. A listing and summary of randomized participants not receiving study drug will be provided. All participants who discontinue the study and/or study drug will be identified, and the extent of their participation in the study will be reported. If known, a reason for their discontinuation will be given. The primary reasons for discontinuation will be listed and summarized by treatment groups.

Details about the demographic and baseline characteristics, historical illnesses, and preexisting conditions, treatment compliance, concomitant medications, and important protocol deviations can be found in Appendices 1 through 5 (Section 6.1 through Section 6.5, respectively).

Analysis Type (Analysis Set)	ICE	Strategy to Handle ICE	Assumption for Missingness	Methods to Handle Missing Values at
× • /			U	Endpoints
Time-averaged Lp(a) over Day 60-180 Analysis (FAS)	None	Treatment policy	MAR	There are no ICEs. Missing values will be imputed using all nonmissing data from the same treatment arm.
Time-averaged Lp(a) over Day 30-180, Day 60-180, Day 30-360, and Day 240-360 Analysis (EAS)	"Permanent discontinuation of intervention" and initiation of excluded medications taken during the study or new initiation of Lp(a) modifying medication required to be on a stable regimen prior to treatment per protocol inclusion criteria.	Hypothetical	MAR	Data collected after the ICE will be set to missing. Missing values will be imputed using all nonmissing data (excluding data collected after ICEs) from the same treatment arm.
Lp(a), ApoB, and hsCRP MMRM (EAS)	"Permanent discontinuation of intervention" and initiation of excluded medications taken during the study or new initiation of Lp(a) modifying medication required to be on a stable regimen prior to treatment per protocol inclusion criteria.	Hypothetical	MAR	Data collected after the ICE will be set to missing. Missing values will be imputed using all nonmissing data (excluding data collected after ICEs) from the same treatment arm.

 Table EZEB.4.2.
 Strategy to Handle ICE and Missingness for Efficacy Endpoints

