Analysis Type (Analysis Set)	ICE	Strategy to Handle ICE	Assumption for Missingness	Methods to Handle Missing Values at Endpoints
Lipids parameter MMRM (EAS)	"Permanent discontinuation of intervention" and initiation of excluded medications taken during the study or new initiation of Lp(a) modifying medication required to be on a stable regimen prior to treatment per protocol inclusion criteria.	Hypothetical	MAR	Data collected after the ICE will be set to missing. Missing values will be imputed using all nonmissing data (excluding data collected after ICEs) from the same treatment arm.
Lp(a) categorical analyses logistic regression (EAS)	"Permanent discontinuation of intervention" and initiation of excluded medications taken during the study or new initiation of Lp(a) modifying medication required to be on a stable regimen prior to treatment per protocol inclusion criteria.	Hypothetical	MAR	Data collected after the ICE will be set to missing. Missing values will be imputed using all nonmissing data (excluding data collected after ICEs) from the same treatment arm.

Abbreviations: ApoB = apolipoprotein B; EAS = efficacy analysis set; FAS = full analysis set; hsCRP= highsensitivity C-reactive protein; ICE = intercurrent event; Lp(a)= lipoprotein(a); MAR = missing at random; MMRM = mixed model repeated measures.

Note: For the continuous analysis of clinical laboratory tests, unscheduled measurements are excluded from analysis to reduce bias. The early discontinuation visits are considered scheduled visits.

Study	Participant Population	Baseline Observations	Postbaseline Observations
Period/Analysis			
Туре			
540 Days Study Per	iod		
1.1) Treatment-	All randomized	The baseline period is defined as	Starts after the first dose of
Emergent Adverse	participants who are	the start of screening and ends	study drug and end of the
Events (FAS)	exposed to at least 1 dose	prior to the first dose of study	study period.
	of study drug	drug (Visit 2).	
1.2) Treatment-	All randomized	Baseline will be all scheduled	Postbaseline will be defined
Emergent	participants who are	and unscheduled measurements	as above (1.1). All scheduled
Abnormal Labs	exposed to at least 1 dose	recorded during the baseline	and unscheduled
and Vital Signs	of study drug who have a	period as defined above (1.1).	measurements will be
(FAS)	normal baseline (with		included.
	respect to the direction		
	being analyzed) and a		
	postbaseline observation		

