4.4.2. Main Analytical Approach

The time-averaged endpoints will be analyzed using the MMRM in a manner similar to method in Section 4.3.2 for the "efficacy estimand" as described in Section 1.1.

The following 2 study objectives will be analyzed using MMRM and the associated efficacy estimand:

- percent change from baseline and absolute change from baseline to Days 60, 180, 240, 360, and 540 for
 - o Lp(a)
 - o ApoB, and
 - o hsCRP
- percent change from baseline and absolute change from baseline in
 - o LDL-C
 - o total cholesterol
 - HDL-C, and
 - o TG.

Binary endpoints with missing values imputed by categorizing (Yes, No) the imputed values for the corresponding continuous endpoints as described in Table EZEB.4.2 will be analyzed using a logistic regression model with treatment and high-risk cardiovascular disease strata as fixed effects and the continuous baseline value as a covariate.

Table EZEB.4.5 summarizes the objective, endpoints, analysis approaches, and additional information for the efficacy estimand analyses.

	Relative to the Efficacy	Analysis Conducted in a	
Objectives	Measure	Manner Similar to	Additional Information
To evaluate if	Percent change from	MMRM model in	
LY3819469 is superior to	baseline in time-averaged	Section 4.3.2	
placebo in percent Lp(a)	Lp(a) over		
reduction over	 Days 60-180 		
• Days 60-180	• Days 240-360		
• Days 240-360	• Days 30-180, and		
• Days 30-180,	• Days 30-360		
and			
• Days 30-360			
Compare the effect of	Percent change from	MMRM model described	The continuous clinical
LY3819469 to placebo on	baseline and absolute	in Section 4.4.2	measures, including
cardiovascular biomarkers	change from baseline to		Lp(a), ApoB, and
	Days 60, 180, 240, 360,		hsCRP, may be log
	and 540 for		transformed before
	• Lp(a)		statistical analyses.
	• ApoB		LSM estimates will be
	• hsCRP		plotted by treatment
			through Day 540.
Compare the lipid profile	Percent change from	MMRM model described	The lipid biomarkers
in response to	baseline and absolute	in Section 4.4.2	may be log transformed
LY3819469 versus	change from baseline in		before statistical
placebo	lipid profile		analyses.
	• LDL-C		

 Table EZEB.4.5.
 Efficacy Estimand Analysis

	Relative to the Efficacy	Analysis Conducted in a	
Objectives	Measure	Manner Similar to	Additional Information

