4.11. Changes to Protocol-Planned Analyses

Extend the time periods of interest for first secondary objective regarding time-averaged Lp(a) lowering.

5. Sample Size Determination

The sample size calculation is based on the primary estimand and its endpoint, and the percent change from baseline in time-averaged Lp(a) over Days 60 to 180.

Approximately 254 participants will be randomly assigned in a 1:2:2:2:2 ratio to LY3819469 16 mg 2 doses, 96 mg 2 doses, 400 mg 2 doses, 400 mg 1 dose plus placebo 1 dose, and placebo 2 doses. Assuming a 15% dropout rate, this results in approximately 24 completers for the 16-mg group and 48 completers per arm for the rest of the groups.

Assuming a SD of 20%, and a 2-sided alpha level of 0.05, the completers for each treatment arm will provide >99% power to detect a treatment difference of 70% reduction for the primary endpoint of LY3819469 versus placebo. The sample size was determined appropriate to provide a sufficient amount of safety data.

6. Supporting Documentation

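### The SAP analyses the protocol's secondary efficacy endpoints only under a hypothetical strategy, leaving the protocol's treatment-policy secondary estimand without a committed analysis and the change undeclared

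*SAP*

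**What the plan says.** **Protocol.** Section 9.3.3 states: "The efficacy analyses for the secondary endpoints will use the FAS described in Section 9.3.1". Section 3 uses an estimand similar to the primary one for responses before the second injection, and then says: "For the objectives after Day 180, the treatment discontinuation will be handled by treatment policy strategy". Within the primary estimand it adds: "The concomitant medication use is not considered intercurrent events as it is considered as a part of patient management". Under Section 7.1, a participant who stops study intervention stays in the study and keeps to the visit schedule.

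**SAP.** Section 1.1 defines a treatment-regimen estimand for Days 60-180 only, and adds an efficacy estimand. Section 4.4 applies the efficacy estimand with a hypothetical strategy, "so only data collected before the occurrence of any such ICEs will be used in the estimation". The intercurrent events are permanent discontinuation and new use of excluded or Lp(a)-altering therapy. Section 4.4.1 lists the endpoints treated this way, including the Days 240-360 average, the <125 and <75 nmol/L proportions, and change in Lp(a), ApoB and hsCRP. For the continuous markers, Section 4.4.2 says: "The following 2 study objectives will be analyzed using MMRM and the associated efficacy estimand". In Table EZEB.4.2 the only efficacy row on the FAS is time-averaged Lp(a) over Days 60-180. Every other row is on the EAS, with data after the event set to missing.

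The whole of SAP Section 4.11, on changes from the protocol, reads: "Extend the time periods of interest for first secondary objective regarding time-averaged Lp(a) lowering".

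**The concern.** The two documents target different quantities. Treatment policy asks what happens to participants as randomized, whether or not they take the second dose. The hypothetical strategy asks what would have happened had everyone adhered and started no interfering therapy. If the SAP is followed, results for the protocol's secondary objectives answer the second question, and no prespecified comparison answers the first.

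The gap is small up to Day 180. Only one injection is given in that period, and both documents say discontinuation is then not an intercurrent event, so the sets differ essentially only through newly started therapy. After Day 180 they also differ for anyone who misses dose 2 but stays in follow-up. That touches Days 240, 360 and 540 and the Days 240-360 average, the only time-averaged window lying wholly after dose 2 (Days 30-360 spans it). Protocol Section 4.2 says the study should inform Phase 3 dose, dosing frequency and durability, and these are the time points that bear on dosing frequency and durability.

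The consequence differs by arm. In Arms A to C the hypothetical estimate describes full adherence to two active doses. In Arm D the second injection is placebo, so missing it leaves drug exposure unchanged. SAP Section 4.4 nonetheless counts such a participant as on treatment only to Day 180 and drops the later, still informative, values.

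**Working it through.** **1. The plan's own figures reproduce.** Inputs from Protocol 9.5 and SAP Section 5: N = 254, ratio 1:2:2:2:2, 15% dropout, SD 20 points, effect 70 points, two-sided alpha 0.05.

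- Randomized: 254 × 1/9 = 28.2 (16 mg) and 254 × 2/9 = 56.4 (each other arm).
- Completers: 28.2 × 0.85 = 24.0 and 56.4 × 0.85 = 48.0. Stated: 24 and 48.
- Power for a difference of 70 with SD 20 is about 1.00 for 24 v 48, 48 v 48 and 96 v 48. Stated: >99%.

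Power is therefore not the issue. The question is which effect is estimated.

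**2. The documents side by side.**

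| Secondary endpoint | Protocol | SAP |
|---|---|---|
| Time-averaged Lp(a), Days 240-360 | FAS; treatment policy for discontinuation | EAS; hypothetical |
| Lp(a) <125 and <75 nmol/L | FAS; treatment policy after Day 180 | EAS; hypothetical |
| Percent change in Lp(a), ApoB, hsCRP | FAS; treatment policy after Day 180 | EAS; hypothetical |
| Declared in SAP 4.11 | – | No; only the added time windows |

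**3. Do other FAS outputs fill the gap?** No.

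- SAP 4.3.2 gives plots of percent change, including beyond Day 180.
- SAP 4.8.6 gives by-visit descriptive summaries, shift tables, and a model for selected laboratory tests that it does not name.
- SAP 4.1 describes a mixed model on all scheduled visits, but under the primary efficacy assessment. No FAS contrast after Day 180 is specified.
- The EAS definition in SAP Section 3 has a parenthesis about analysing by assigned treatment after Day 180. It does not restore treatment policy, because Section 4.4 names treatment discontinuation as an intercurrent event for that period.

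**4. Illustration of size (all inputs assumed).** Let r2 be the ratio to baseline after two doses, r1 = r2 + gap the ratio in those who miss dose 2 but stay, and f their share of the arm. Placebo is taken as unchanged. On the SAP's log scale:

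- hypothetical ratio = r2
- treatment-policy ratio = r2^(1−f) × r1^f
- shift in points = 100 × (treatment-policy ratio − r2)

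With r2 = 0.30, matching the 70% planning effect:

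- f = 0.05, gap 0.20: 0.30 × (0.50/0.30)^0.05 = 0.3078, a shift of 0.8 points.
- f = 0.15, gap 0.40: 0.30 × (0.70/0.30)^0.15 = 0.3407, a shift of 4.1 points.

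| r2 | f = 0.05, gap 0.20 | f = 0.15, gap 0.40 |
|---|---|---|
| 0.10 | 0.56 | 2.73 |
| 0.30 | 0.78 | 4.07 |
| 0.50 | 0.85 | 4.61 |

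In Arms B and C, 5-15% of 56.4 is 2.8 to 8.5 participants.

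A cruder linear version lets 2-15% miss dose 2 and lose 25-100% of a 70-point effect. The shift is then 70 × 0.02 × 0.25 = 0.35 up to 70 × 0.15 × 1 = 10.5 points. Even at 59.5 points, power for 24 v 48 remains about 1.00.

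**The case against.** The best defence has four parts.

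- **The change is open and permitted.** SAP 1.1 defines and motivates the efficacy estimand, the analyses are labelled with it, and Protocol 9.3.1 lets changes that are not a principal feature be described and justified in the SAP or the study report. It stands that a reader can tell which estimand is used. But nothing says that it replaces the protocol's secondary estimand, or why, and a later note in the report cannot supply a prespecified FAS contrast. The SAP version history should not count as a second omission, since it records changes between SAP versions.
- **FAS information after Day 180 exists.** This is true descriptively, and the Section 4.1 model would include later visits. None of it commits to a comparison for a secondary endpoint.
- **The protocol's secondary estimand is loosely worded.** It is only called similar to the primary one, and the sentence on events after Day 180 covers discontinuation alone. Extending the concomitant-medication rule beyond Day 180 is inference. The conflict over discontinuation and over the analysis set does not depend on that inference.
- **The consequence is limited.** Protocol 7.2 expects discontinuation to be uncommon, the secondary endpoints carry no multiplicity control, and an adherence-based effect is a defensible target for Phase 2 dose selection. Missed drug exposure at Day 180 cannot arise in Arms D and E, 4/9 of participants. This limits the size and is a reason to keep the EAS analyses, but it does not make the documents agree.

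**Conclusion.** The concern holds. As written, the SAP leaves the protocol's secondary estimand without a committed inferential analysis, and Section 4.11 does not say so. It should be fixed. The primary endpoint is unaffected.

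The size is unknown. The documents give no rate of missed second doses with continued follow-up; the 15% dropout figure is a different quantity. Across the log-scale scenarios shown, the hypothetical estimate is more favourable by about 0.6 to 4.6 points. The linear version, whose upper end assumes complete loss of effect, reaches 10.5. All of this rests on assumed shares, gaps and ratios, and on a smaller reduction in those who miss dose 2. It covers percent change in Lp(a) and missed second doses only. The effect of newly started therapy, and the ApoB, hsCRP and threshold endpoints, are not quantified.

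**What to change.** 1. Add FAS/treatment-policy rows to Table EZEB.4.2, with matching text in the analysis sections, for the protocol's secondary efficacy endpoints, at least those after Day 180. Use all data collected after discontinuation or new medication.
2. Report these as the analyses of the protocol's secondary objectives, alongside the EAS analyses. If the EAS analyses are to lead, keep the FAS versions as prespecified and justify the choice.
3. In either case, declare the added efficacy estimand and the EAS in Section 4.11 as departures from the protocol.
4. Reword the parenthesis on post-Day 180 analysis in the EAS definition (SAP Section 3) so that it cannot be read against Section 4.4.

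The cost is SAP wording and re-running the same models on the FAS. No new data are needed, because Protocol 7.1 already keeps these participants in follow-up.

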4.4.2. Main Analytical Approach

The time-averaged endpoints will be analyzed using the MMRM in a manner similar to method in Section 4.3.2 for the "efficacy estimand" as described in Section 1.1.

The following 2 study objectives will be analyzed using MMRM and the associated efficacy estimand:

- percent change from baseline and absolute change from baseline to Days 60, 180, 240, 360, and 540 for
 - o Lp(a)
 - o ApoB, and
 - o hsCRP
- percent change from baseline and absolute change from baseline in
 - o LDL-C
 - o total cholesterol
 - HDL-C, and
 - o TG.

Binary endpoints with missing values imputed by categorizing (Yes, No) the imputed values for the corresponding continuous endpoints as described in Table EZEB.4.2 will be analyzed using a logistic regression model with treatment and high-risk cardiovascular disease strata as fixed effects and the continuous baseline value as a covariate.

Table EZEB.4.5 summarizes the objective, endpoints, analysis approaches, and additional information for the efficacy estimand analyses.

	Relative to the Efficacy	Analysis Conducted in a	
Objectives	Measure	Manner Similar to	Additional Information
To evaluate if	Percent change from	MMRM model in	
LY3819469 is superior to	baseline in time-averaged	Section 4.3.2	
placebo in percent Lp(a)	Lp(a) over		
reduction over	 Days 60-180 		
• Days 60-180	• Days 240-360		
• Days 240-360	• Days 30-180, and		
• Days 30-180,	• Days 30-360		
and			
• Days 30-360			
Compare the effect of	Percent change from	MMRM model described	The continuous clinical
LY3819469 to placebo on	baseline and absolute	in Section 4.4.2	measures, including
cardiovascular biomarkers	change from baseline to		Lp(a), ApoB, and
	Days 60, 180, 240, 360,		hsCRP, may be log
	and 540 for		transformed before
	• Lp(a)		statistical analyses.
	• ApoB		LSM estimates will be
	• hsCRP		plotted by treatment
			through Day 540.
Compare the lipid profile	Percent change from	MMRM model described	The lipid biomarkers
in response to	baseline and absolute	in Section 4.4.2	may be log transformed
LY3819469 versus	change from baseline in		before statistical
placebo	lipid profile		analyses.
	• LDL-C		

 Table EZEB.4.5.
 Efficacy Estimand Analysis

	Relative to the Efficacy	Analysis Conducted in a	
Objectives	Measure	Manner Similar to	Additional Information
